6.1 Overview of Study Design

This is a Phase 4, open-label, repeat-dose, parallel-design study in 12 subjects with severe hepatic impairment (MELD 19 to 25 and MELD >25) and 6 healthy subjects with normal hepatic function. At least 6 hepatically impaired subjects will have MELD score >25. Efforts will be made to match subjects across groups in terms of age, weight, and sex. Eligible subjects will complete a Screening Period of up to 21 days prior to dosing (Day 1), a 7-day Treatment Period, and Follow-Up by phone 3 (+1) days later. Subjects will be admitted to the Clinical Research Unit (CRU) on the day prior to the initiation of dosing (Day -1; CRU admission). A plasma sample for PK analysis will be collected on Day 1 prior the first dose. Subjects will receive 550 mg rifaximin BID approximately 12 hour apart for 6 days beginning on Day 1 (Baseline). On Day 7 (End of Treatment; EOT), the final dose of study drug will be administered in the morning following an overnight fast of 10 hours and plasma samples for PK analysis will be collected pre-dose (within 1 hour of the dose) and at 0.25, 0.5, 0.75, 1, 1.5, 2, 4, 6, 8, 10, 12, 16, 20, and 24 hours post-dose. Additionally, a trough blood sample will be collected on Days 2-6, prior to administration of the first daily

Clinical Study Protocol Amendment 1 08Oct2018

dose of rifaximin. Subjects will reside in the CRU for 9 days and will be discharged following the final PK sample collection if safety parameters are acceptable to the Investigator. Each subject will be contacted for a follow-up phone call 3 + 1 days following end of treatment. The study schematic is presented in Figure 1.

Each dose will be administered with a total of 240 mL of water. During the first 4 hours after dose administration, subjects should not lie flat; they should be allowed to sit or stand. Subjects will receive standardized meals while in the CRU.

Subjects will discontinue non-study rifaximin on Day -1 and will only use rifaximin provided as study drug by the sponsor during the Treatment Period. Subjects may resume their prescription rifaximin use following CRU discharge.

Stool samples for microbiome analysis will be collected in the Screening Period and on Day 7 or 8.

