- 14. Subject is anemic, as defined by hemoglobin of $\leq 8 \text{ g/dL}$.
- 15. Subject has significant hypovolemia, or any electrolyte abnormality that can affect mental function (e.g., serum sodium <125 mmol/L, serum calcium >10 mg/dL).
- 16. Subject has severe hypokalemia as defined by a serum potassium level <2.5 mmol/L.
- 17. Subject's current, required medications are prohibited concurrent medications per protocol. Subjects will discontinue non-study rifaximin on Day -1 and will only use rifaximin provided as study drug by the sponsor during the Treatment Period through CRU discharge.
- 18. Subject is positive for *Clostridium difficile* toxin via stool examination at Screening. NOTE: Results of stool tests must be confirmed as negative for Toxins A and B prior

to Day -1. A stool sample must be collected during the Screening Period. Testing will be performed by enzyme immunoassay (EIA).

- 19. Subject has an acute illness within 1 week of CRU admission.
- 20. Subject has donated plasma within 7 days of drug administration.
- 21. Subject has donated 1 or more pints of blood (or equivalent blood loss) within 30 days prior to drug administration.
- 22. The subject has known or suspected illicit drug use within the past year, or positive findings on urine drug screen (except for allowed prescription medications), or has used any tobacco or nicotine products during the 6 months prior to screening and does not agree to refrain from using tobacco or nicotine products during the study.
- 23. The subject has received any type of vaccination within 7 days of drug administration.
- 24. Subject reports consumption of more than 2 alcoholic drinks daily, more than 14 alcoholic drinks within 14 days before the screening evaluation (an alcoholic drink is defined as 1.5 oz liquor, one 12 oz can of beer, or 5 oz of wine), or consumption of any alcohol within 24 hours of first drug administration.
- 25. The subject has consumed grapefruit juice, grapefruits, or Seville oranges within 24 hours of first drug administration and does not agree to refrain from consuming these foods during the study.

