8.3.1 Prohibited Therapy

Use of the following medications is prohibited within the inclusion/exclusion specified prestudy timeframes and throughout the study unless otherwise noted:

- Milk thistle within 30 days of Day 1 (Baseline).
- Investigational drugs within 30 days of Day 1 (Baseline).
- Daily prophylactic antibiotics within 30 days of Day 1 (Baseline).

The following concomitant medications are prohibited after Screening and throughout the study:

- Non-study rifaximin (200 mg or 550 mg tablets) is prohibited beginning Day 1 and throughout the Treatment Period. Subjects may resume their prescription rifaximin use following CRU discharge.
- Psychoactive, neuroactive agents (except as allowed per protocol) and psychotropic drugs.
- Warfarin-type anticoagulants.
- Rifampin or other rifamycin derivatives (except study drug).
- Alternative, herbal or complementary therapies for liver cirrhosis other than those required to manage fluid and electrolyte homeostasis.

Consumption of certain foods and substances that are known to inhibit and/or induce CYP are not permitted during this study as specified in exclusion criteria. (See Appendix 16.2 or http://medicine.iupui.edu/clinpharm/ddis/main-table for a complete listing of excluded potential CYP inducers/inhibitors).

All over the counter and prescription medications are prohibited for healthy subjects. If any medication is required during the study for healthy subjects, the subject may be discontinued from the study at the discretion of the Investigator or the Sponsor.

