10.1 Schedule of Evaluations and Procedures

10.1.1 Screening (Day -21 to Day -2)

After signing the informed consent, patients will undergo the screening procedures to confirm eligibility to participate in the study.

During Screening, the following procedures/assessments will be performed:

- Obtain written informed consent prior to performing any study evaluations.
- Assign subject identification number.
- Record medical history and demographic information (date of birth, sex, ethnicity, and race), including verification of tuberculosis history. Note: Efforts will be made to match subjects across groups for age, weight and sex.
- Review subject eligibility.
- Assessment of MELD score and Child-Pugh classification (A, B, or C).
- Perform physical examination.
- Measure height and weight. Height and weight will be used to calculate body mass index (BMI).

- Perform vital signs (oral temperature, seated blood pressure and pulse). Subjects should be allowed to rest in the seated position for approximately 5 minutes prior to collection of blood pressure and pulse.
- Obtain 12-lead ECG. Assessments for clinically significant findings may be repeated if necessary.
- Collect samples for laboratory tests:
 - Blood samples for hematology, chemistry, coagulation, and testing for tuberculosis, HIV, hepatitis B surface antigen, and hepatitis C virus.
 - Blood sample for serum pregnancy testing for females of childbearing potential. A negative pregnancy test must be confirmed prior to check-in on Day -1.
 - Urine for a urine pregnancy test for females of child-bearing potential. A negative pregnancy test must be confirmed to continue participation in the study.
 - Urine samples for urinalysis and urine drug/nicotine/alcohol screen.

NOTE: Blood sample collection for the clinically significant laboratory results may be repeated, if necessary. Results from all laboratory tests must be received and reviewed prior to CRU check-in on Day -1.

- Record any AEs and SAEs since the time of informed consent.
- Record concomitant medications.
- Stool collection and processing for:
 - Presence of enteric infections (this stool sample analysis must be available prior to check-in on Day -1).
 - Microbiota characterization.

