- NOTE: If the subject cannot produce a stool sample at Screening, dispense a stool sample kit and instruct subjects on collection of the stool sample to be returned to the site at least 7 days prior to Day -1. The results for the stool sample are needed before check-in to the CRU.

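### Impaired subjects still taking prescription rifaximin at the Screening stool have an on-drug baseline, and Section 12.6.2 does not separate them, so a combined before/after summary could understate the change.

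*Combined protocol and SAP*

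**What the plan says.** Each subject gives two stools for the microbiome work (Section 6.1): "Stool samples for microbiome analysis will be collected in the Screening Period and on Day 7 or 8". The Screening stool is the only one before study treatment. Section 10.1.1 and the schedule in Section 16.1 place Screening at Day -21 to Day -2. There is a home-kit route in Section 10.1.1: "If the subject cannot produce a stool sample at Screening, dispense a stool sample kit", and staff are to "instruct subjects on collection of the stool sample to be returned to the site at least 7 days prior to Day -1".

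On prescription rifaximin, Section 6.1 says: "Subjects will discontinue non-study rifaximin on Day -1 and will only use rifaximin provided as study drug by the sponsor during the Treatment Period". Exclusion criterion 17 for impaired subjects (Section 7.1.2) repeats the Day -1 stop. Section 8.3.1 says: "Non-study rifaximin (200 mg or 550 mg tablets) is prohibited beginning Day 1 and throughout the Treatment Period". The protocol expects some subjects to be established users, since Section 6.1 adds: "Subjects may resume their prescription rifaximin use following CRU discharge".

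Three other provisions bear on the same question. Section 8.3 bars medication in general from 14 days before dosing, with an exception at the investigator's decision. Criterion 10 in Section 7.1.2 excludes subjects who need daily prophylactic antibiotics. Section 8.3.1 bars such antibiotics within 30 days of Day 1.

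The exploratory objective (5.2) concerns the effect of giving rifaximin on the microbiome in severe hepatic impairment. The endpoint (5.5) compares samples from before and after the study week. Section 12.6.2 plans descriptive summaries of counts, species and resistance and does not mention earlier or current rifaximin use. Section 12 leaves the detailed specifications to a SAP that is to be final before database lock.

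**The concern.** A before/after comparison needs a baseline free of the treatment. For a subject on prescription rifaximin at the Screening stool, both samples are taken on the drug, and the difference describes staying on rifaximin. If such subjects are summarized together with subjects who start rifaximin on Day 1, the average change shrinks towards zero, and a small change may be read as a small effect.

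Resistance has a related problem. Resistance selected by earlier use can already be present in the baseline, so a baseline containing users does not describe an unexposed flora. Resistance that first appears during the study week would still show.

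The issue is essentially confined to impaired subjects, who are the group named in Section 5.2. Healthy subjects must avoid prescription drugs for 14 days before admission unless authorized (Section 7.2.1, criterion 9).

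**Working it through.** The plan gives no figure for this endpoint (no effect size, power or precision), so there is nothing to reproduce. The check has three steps.

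**1. Day order.** There is no Day 0; Day -1 is the day before Day 1. Screening from Day -21 to Day -2 is 20 days. A home-kit stool is due 7 days before Day -1, that is by Day -8, so its window is Day -21 to Day -8, or 14 days. The share of days on which a current user's stool would be on-drug depends on which text governs:

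| Reading | Any Screening stool | Home-kit stool |
|---|---|---|
| Rifaximin-specific text (6.1; 7.1.2 criterion 17; 8.3.1): stop on Day -1 | 20 of 20 days | 14 of 14 days |
| 14-day ban in 8.3 also covers rifaximin: stop by Day -14 | 7 of 20 (Day -21 to -15) | 7 of 14 |
| Daily prophylactic antibiotic bars (criterion 10; 30 days in 8.3.1) cover rifaximin | 0 of 20 | 0 of 14 |

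Under the second reading, the other 13 days fall 0 to 12 days after the stop, or 0 to 6 days after it for the kit. Section 8.3.1 also bars rifamycin derivatives, but only after Screening, so that bar does not reach this sample.

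**2. Dilution of a mean change.** Let f be the share of impaired subjects on rifaximin at the Screening stool, and r the share of the effect already present in them. The documents give neither, so both are assumptions. If off-drug subjects change by D on average, users change by (1 − r)D, and the combined mean change is

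(1 − f)D + f(1 − r)D = D(1 − f·r), so observed/true = 1 − f·r.

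| On rifaximin at Screening stool, of 12 | f | r = 0.25 | r = 0.5 | r = 1 |
|---|---|---|---|---|
| 0 | 0 | 1.00 | 1.00 | 1.00 |
| 3 | 0.25 | 0.94 | 0.875 | 0.75 |
| 6 | 0.50 | 0.875 | 0.75 | 0.50 |
| 9 | 0.75 | 0.81 | 0.625 | 0.25 |

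Under the 14-day reading, assume that stools are spread evenly over the 20 days and that nothing persists after the stop. Then 7/20 = 35% of users' stools are on-drug, and f is replaced by 0.35 × (users/12):

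- r = 1, with 3, 6 or 9 users: 1 − 0.0875, 1 − 0.175, 1 − 0.2625 = 0.91, 0.825, 0.74.
- r = 0.5: 0.96, 0.91, 0.87.

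If every stool came by home kit, spread evenly over its 14 days, the share would be 7/14 = 50%. At r = 1 the ratios would then be 0.875, 0.75 and 0.625.

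This model fits a mean such as log counts. It does not carry over to species listings, 16S composition and diversity, or MIC results.

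**3. Precision after a split.** The 95% half-width for a mean change, in SD units, is t(0.975, n − 1)/√n:

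| n | 12 | 9 | 6 | 3 | 2 |
|---|---|---|---|---|---|
| Half-width (SD) | 0.64 | 0.77 | 1.05 | 2.48 | 8.98 |

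Crossing the flag with the two MELD strata gives 12/4 = 3 subjects per cell on average.

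**The case against.** The strongest reply is that the plan has not yet chosen to pool. Section 12.6.2 is brief, it never says users and non-users will be combined, and the SAP is where such detail belongs. That is true, and it makes the harm conditional. But no text in the documents commits to a split, and following Section 12.6.2 as written would mix on-drug and off-drug baselines.

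Second, users may not be eligible at all. If daily rifaximin counts as a prophylactic antibiotic, the 30-day bar covers the whole Screening window and the bias is zero. Rifaximin is also absent from the list of medications that Section 8.3 allows impaired subjects. Against this, the sentences on the Day -1 stop and on resuming after discharge would then have little purpose. The documents do not settle the matter, which is a reason to reconcile them.

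Third, f and r are assumed, and the ratios run from 1.00 to 0.25. That stands: the tables show how the bias would behave and do not estimate it.

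Fourth, Section 4.2 says the effect on colonic flora is not clinically significant, so there may be little change to dilute. That is background text, and it does not make an on-drug sample a baseline for the question in Section 5.2.

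Fifth, the endpoint in Section 5.5 can be read as referring only to the study course, which users do receive. The objective in Section 5.2 is broader, and for users the comparison does not answer it.

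**Conclusion.** The concern holds. Under the rifaximin-specific text every Screening stool precedes the stop, so a current user's baseline is on-drug. Under the 14-day reading this still applies on 7 of the 20 Screening days. Section 12.6.2 does not tell these subjects apart.

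The size cannot be derived from the documents. It is zero if no users enrol, which includes the case where the daily-antibiotic bars exclude them. The illustrative ratios also assume the same underlying effect in users and non-users. Priority is low to moderate: the endpoint is exploratory and descriptive, and this point does not affect the primary pharmacokinetic objective.

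**What to change.** In Section 12.6.2 or the SAP, before database lock:

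- Flag each impaired subject as on or not on rifaximin at the Screening stool, using the stool date and the medication start and stop dates already recorded (8.3, 10.5.4).
- Present before/after counts, composition and resistance by that flag. Where a subset is very small, and in any cross with MELD stratum, use by-subject listings that carry the flag.
- Label the users' comparison as continued treatment, and do not interpret a combined change as the effect of starting rifaximin.
- State the limits. Courses that ended before Screening may not be captured, so the not-on-rifaximin group can include recent users. Permitted weekly antibiotics and laxatives also act on the stool. There is no untreated comparator, so the split does not isolate a drug effect.

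Separately, the rifaximin-specific text (6.1, 7.1.2 criterion 17, 8.3.1), the 14-day ban (8.3) and the daily prophylactic antibiotic bars (7.1.2 criterion 10, 8.3.1) must be reconciled. No position is taken here on which is right.

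The analysis change costs one derived flag and one split or listing, with no change to treatment, visits or samples. The drawback is small cells.

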7.1 Inclusion/Exclusion for Subjects with Severe Hepatic Impairment

7.1.1 Hepatic Impairment Subject Inclusion Criteria

A subject will be eligible for inclusion in this study if all of the following criteria are met:

- 1. Subject provides written informed consent as documented on the Institutional Review Board (IRB) approved informed consent document.
- 2. Subject is ≥ 18 years of age at Screening.
- 3. Male or non-pregnant, non-breast feeding female.

Clinical Study Protocol Amendment 1 08Oct2018 4. Females of childbearing (reproductive) potential must have a negative serum pregnancy test at Screening and a negative urine pregnancy test at Screening and Day 1, and agree to use an acceptable method of contraception throughout their participation in the study. Examples of acceptable methods of contraception include double barrier methods (condom with spermicide jelly or diaphragm with spermicide), hormonal methods (oral contraceptives, patches or medroxyprogesterone acetate), or an intrauterine device with a documented failure rate of less than 1% per year. Abstinence may be considered an acceptable method of contraception at the discretion of the investigator.

NOTE: Females who have been surgically sterilized (e.g., hysterectomy or bilateral tubal ligation) or who are postmenopausal (total cessation of menses for >1 year) will not be considered "females of childbearing potential."

- 5. Subject has a diagnosis of liver cirrhosis.
- 6. Subject has a MELD score of ≥19 at Screening. Note: At least 6 subjects will have a MELD score of >25.
- 7. Subject is capable of understanding the requirements of the study, is willing to comply with all the study procedures, and is willing to attend all study visits.

7.1.2 Hepatic Impairment Subject Exclusion Criteria

A subject will **not** be eligible for inclusion in this study if any of the following criteria are met:

- 1. Subject has known allergy to rifaximin, rifampin, or other rifamycins, or to excipients and/or vehicles used in the formulation or other clinically significant allergies.
- 2. Subject has participated in an investigational drug or device study within the 30 days prior to Day 1 (Baseline).
- 3. Subject is an employee of the site that is directly involved in the management, administration, or support of this study or is an immediate family member of the same.
- 4. Subject has any concurrent illness (other than liver cirrhosis), disability or circumstance that may affect the interpretation of clinical data, could cause noncompliance with treatment or visits or otherwise contraindicates participation in this study in the opinion of the investigator.
- 5. Subject is pregnant or at risk of pregnancy, or is lactating.

- 6. Subject has a history of tuberculosis infection or has received treatment for a tuberculosis infection. To rule out tuberculosis infection, any one of the following criteria must apply: a) negative tuberculin skin test or negative tuberculosis blood test or b) if a subject has had a previous positive test, they must have a current negative chest X-ray (within 6 months of enrollment), or a current negative blood tuberculosis test.
- 7. Subject is positive for human immunodeficiency virus (HIV), hepatitis B and/or hepatitis C on Screening assessments.
- 8. Subject has been diagnosed with chronic respiratory insufficiency that in the opinion of the investigator would prevent completion of the study, interfere with analysis of study results, or negatively impact the subject's participation in the study.
- 9. Subject has renal insufficiency requiring routine dialysis.
- 10. Subject has an active spontaneous bacterial peritonitis infection or subject requires daily prophylactic antibiotic therapy.
- 11. Subject shows presence of intestinal obstruction or has inflammatory bowel disease.
- 12. Subject has an active malignancy within the last 5 years (exceptions basal cell carcinomas of the skin, or if female, in situ cervical carcinoma that has been surgically excised).
- 13. Subject has current GI bleeding or has had a GI hemorrhage of sufficient severity to require hospitalization and a transfusion of ≥ 2 units of blood within 3 months prior to Screening.
- 14. Subject is anemic, as defined by hemoglobin of $\leq 8 \text{ g/dL}$.
- 15. Subject has significant hypovolemia, or any electrolyte abnormality that can affect mental function (e.g., serum sodium <125 mmol/L, serum calcium >10 mg/dL).
- 16. Subject has severe hypokalemia as defined by a serum potassium level <2.5 mmol/L.
- 17. Subject's current, required medications are prohibited concurrent medications per protocol. Subjects will discontinue non-study rifaximin on Day -1 and will only use rifaximin provided as study drug by the sponsor during the Treatment Period through CRU discharge.
- 18. Subject is positive for *Clostridium difficile* toxin via stool examination at Screening. NOTE: Results of stool tests must be confirmed as negative for Toxins A and B prior

to Day -1. A stool sample must be collected during the Screening Period. Testing will be performed by enzyme immunoassay (EIA).

- 19. Subject has an acute illness within 1 week of CRU admission.
- 20. Subject has donated plasma within 7 days of drug administration.
- 21. Subject has donated 1 or more pints of blood (or equivalent blood loss) within 30 days prior to drug administration.
- 22. The subject has known or suspected illicit drug use within the past year, or positive findings on urine drug screen (except for allowed prescription medications), or has used any tobacco or nicotine products during the 6 months prior to screening and does not agree to refrain from using tobacco or nicotine products during the study.
- 23. The subject has received any type of vaccination within 7 days of drug administration.
- 24. Subject reports consumption of more than 2 alcoholic drinks daily, more than 14 alcoholic drinks within 14 days before the screening evaluation (an alcoholic drink is defined as 1.5 oz liquor, one 12 oz can of beer, or 5 oz of wine), or consumption of any alcohol within 24 hours of first drug administration.
- 25. The subject has consumed grapefruit juice, grapefruits, or Seville oranges within 24 hours of first drug administration and does not agree to refrain from consuming these foods during the study.

